Update 6/6/2025: We decided to add Sankey plots to explore the numbers and patterns of people in each treatment arm whose SBP measurements are in control (version 1: SBP $<$ 140, version 2: SBP $<$ 130), out of control (version 1: SBP \geq 140, version 2: SBP \geq 130), or missing at baseline, 4 months, 8 months, and 120 months.

Table Shells and Data Visualizations: Description on how to present demographic and clinical characteristics (“Table 1”) and study aim or hypothesis data.

Table 1: Patient characteristics (e.g., demographics, medical history) overall and by treatment arm

Supplemental Table 1: Patient blood pressure and cholesterol values at each time point, overall and by treatment arm

Table 2: Primary and secondary outcomes at each time point by treatment arm

Figure 1: STROBE or CONSORT*

Table 3: Intervention effects (LMM) on primary and secondary outcomes

Figure 2: Model-estimated effects and 95% CIs over time

Supplemental Table 2 (if needed): Sensitivity analysis (missing data) of intervention effects on primary and secondary outcomes

Table 4: Subgroup analyses (moderation effects): clinic site, sex, baseline ASCVD risk category

Figure 3: Sankey plots of in/out of control SBP at each visit by treatment arm

Table 1. Patient characteristics at baseline, overall and by treatment arm

Variable	Treatment Arm		Overall (N=XXX)
	Control (N=XXX)	Treatment (N=XXX)	
Enrollment Site			
Hyperlipidemia			
Sex			
Gender			
Sexual Orientation			
Race			
Ethnicity			
Education			

Some of these are specific to clinical trials (based on this [JAMA paper](#)) and some are other are specific to observational studies (based on [STROBE/RECORD](#) guidelines),

Statistical Analysis Plan

Project: A nurse-led intervention to extend the Veteran HIV treatment cascade for cardiovascular disease prevention (V-EXTRA-CVD)

Principal Investigators: [name] PhD

Deliverable (e.g., manuscript, report): Manuscript

Employment Status			
Marital Status			
Financial Status			
Housing or Food Insecurity			
Rurality			
Smoking Status			
Age			
Time since HIV diagnosis (years)			
10-year ASCVD risk score			
ADI National Rank			
ADI State Rank			
Chaos Total Score			
Loneliness Total Score			

Supplemental Table 1. Patient blood pressure and cholesterol values at each time point, overall and by treatment arm

Variable	Treatment Arm		Overall
	Control	Treatment	
Baseline			
SBP (N=XXX)			
DBP (N=XXX)			
Non-HDL (N=XXX)			
Cholesterol (N=XXX)			
HDL (N=XXX)			
LDL (N=XXX)			
4 Month			
SBP (N=XXX)			
DBP (N=XXX)			
Non-HDL (N=X XX)			
Cholesterol (N=XXX)			
HDL (N=XXX)			
LDL (N=XXX)			
8 Month			
SBP (N=XXX)			
DBP (N=XXX)			
Non-HDL (N=XXX)			
Cholesterol (N=XXX)			
HDL (N=XXX)			
LDL (N=XXX)			
12 Month			
SBP (N=XXX)			
DBP (N=XXX)			
Non-HDL (N=XXX)			

Some of these are specific to clinical trials (based on this [JAMA paper](#)) and some are other are specific to observational studies (based on [STROBE/RECORD](#) guidelines),

Statistical Analysis Plan

Project: A nurse-led intervention to extend the Veteran HIV treatment cascade for cardiovascular disease prevention (V-EXTRA-CVD)

Principal Investigators: [name] PhD

Deliverable (e.g., manuscript, report): Manuscript

Cholesterol (N=XXX)				
HDL (N=XXX)				
LDL (N=XXX)				

Table 2. Model-estimated outcome means and standard errors at each time point by treatment arm

	Baseline		4 Months		8 Months		12 Months	
	Intervention Mean (SE)	Control Mean (SE)						
Primary Outcome								
SBP, mmHg								
Secondary Outcome								
Non-HDL cholesterol, mg/dL								

Table 3. Intervention effects (LMM) on primary and secondary outcomes

Outcomes	4 Months		8 Months		12 Months		P-value
	Mean Difference (95% CI)	P-value	Mean Difference (95% CI)	P-value	Mean Difference (95% CI)	P-value	
Primary Outcome							
SBP, mmHg							
Secondary Outcome							
Non-HDL cholesterol, mg/dL							

Supplemental Table 2. Intervention effects (LMM) on primary and secondary outcomes in multiple imputation sensitivity analysis*

Outcomes	4 Months		8 Months		12 Months		P-value
	Mean Difference (95% CI)	P-value	Mean Difference (95% CI)	P-value	Mean Difference (95% CI)	P-value	
Primary Outcome							
SBP, mmHg							
Secondary Outcome							
Non-HDL cholesterol, mg/dL							

*Covariates associated with missingness at any time point were XXX.

Table 4. Moderation Effects of Sex, Clinic, and ASCVD Risk

		Intervention Effect
--	--	---------------------

Some of these are specific to clinical trials (based on this [JAMA paper](#)) and some are other are specific to observational studies (based on [STROBE/RECORD guidelines](#)),

Statistical Analysis Plan

Project: A nurse-led intervention to extend the Veteran HIV treatment cascade for cardiovascular disease prevention (V-EXTRA-CVD)

Principal Investigators: [name] PhD

Deliverable (e.g., manuscript, report): Manuscript

Moderator	Outcomes	Overall joint test	4 Months		8 Months		12 Months	
		P-value	Beta (95% CI)	P-value	Beta (95% CI)	P-value	Beta (95% CI)	P-value
Sex (Reference: Male)	Primary Outcome SBP, mmHg							
	Secondary Outcome Non-HDL cholesterol, mg/dL							
Clinic (Reference: Durham)	Primary Outcome SBP, mmHg							
	Secondary Outcome Non-HDL cholesterol, mg/dL							
ASCVD Risk (Reference: Low-Risk)	Primary Outcome SBP, mmHg							
	Secondary Outcome Non-HDL cholesterol, mg/dL							

Some of these are specific to clinical trials (based on this [JAMA paper](#)) and some are other are specific to observational studies (based on [STROBE/RECORD](#) guidelines),

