**Subsequent visits: (4,8,12 months)**

- Have in-office BP obtained by a trained research assistant using a standardized protocol mentioned above.
- Complete health-related surveys (see full list of measures in section 5.5). Surveys may also be administered by telephone or by mail if Veteran is unable to complete the research visit in-person, but priority will be given to in-person survey administration.
- Measurement of vitals: weight, waist circumference
- Have blood drawn at VA lab to measure lipid panel. If lipid panel has been completed in the past 28 days, will not need to repeat during follow-up visit.

**Randomization:** Study statisticians will develop a 1:1 blocked randomization scheme, stratified by site and hyperlipidemia status. The project coordinator and research assistant will be blinded to the randomization schema and will randomize each subject using an automated randomization methods embedded in the study tracking software. Participants will be randomized to one of two groups:

- Education control group
- Intervention

[figure not shown]
**Education control group:** Participants assigned to the education group at baseline will receive usual care enhanced with general prevention education delivered by the research assistant in person at lab collection times (0, 4, 8, and 12 months). Providers will not be able to see research outcome assessment of BPs since these are not placed into CPRS.

We believe it would be unethical to use a usual care comparison group. The Education control group is receiving more than usual care: education material given at each visit, BP monitored and documented in CPRS, and providers notified if BP exceeds safety thresholds, requiring their co-signature.

**Intervention:** Participants assigned to the intervention will also complete in-person visits every 4 months, as listed above but will also have additional contact with our interventionist who may be either a nurse or pharmacist. The in-person visits will be identical to those in the education control group, but without the in-person education material. At their baseline visit, individuals enrolled in the intervention will be invited to consent and enroll in the VA Annie program, allowing them to submit home BP readings via text message before their intervention contacts. This is an existing VA program, but will not be required to participate in the intervention.

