High Cholesterol	High Blood Pressure
Hyperlipidemia	Hypertension
Dyslipidemia	Essential Hypertension
Hypertriglyceridemia	Secondary Hypertension
Hypercholesterolemia	Hypertensive end-organ disease
Elevated LDL	High blood pressure
Elevated Triglycerides	
Elevated Cholesterol	
Familial Hypercholesterolemia	

DO NOT include the following:	DO NOT include the following:
Low HDL	Pulmonary hypertension
	Intracranial hypertension
	Venous hypertension
	Pre-eclampsia or Maternal Hypertension
	Portal hypertension
	Ocular hypertension

Specific recruitment strategies may vary at each site depending on the preferences of the clinic providers and Veteran populations, but will include a mix of the following methods:

1. The research team will mail introductory letters to Veterans who meet eligibility criteria using a strategy whereby Veterans may call to opt out. The letters are on VAMC letterhead and signed by the study site PIs.
2. Medical providers in their clinics may talk to their patients about the study and refer potentially eligible and interested patients to the site's research assistant.
3. Study-specific flyers and brochures will be made available at each of the site's clinics, allowing Veterans to self-select and call the research team for more information.

The research assistant will contact potentially eligible Veterans and administer a screening questionnaire to further assess eligibility. This may be done by phone, or in-person (if a patient is already on-site for an appointment and able to meet with the research team). If patients meet screening criteria and are interested in participating, we will schedule an enrollment visit to coincide with an upcoming clinic appointment or the availability of the Veteran. If  $\geq 30$  days pass between initial chart review and date of consent, chart review may be repeated to confirm eligibility at time of consent.

All enrolled participants will complete a baseline assessment which includes in-office BPs, lipid panels, and several health-related surveys (see section 5.5 study evaluations). On return visits at 4, 8 and 12 months all participants will similar assessments. Participants will be randomized during the baseline visit.

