## **5.3 Informed Consent Procedures**

Subjects for each aim will go through the informed consent process to participate in the study. Research staff (RA or PC) will read, review, and discuss consent documents with all potential participants prior to obtaining consent. If the veteran appears confused or indicates a lack of understanding, the interviewer will attempt to identify the misunderstanding and to explain the study again. Any veteran who still does not comprehend the consent process and study will be excluded from the study. Veterans who understand the consent process and study and agree to participate in the study will be asked to provide consent either verbal or written. For those participants who provide written informed consent, the research assistant will keep the original signed and dated consent documents and will provide a copy of the signed documents to the subject. No veterans who have impaired decision-making abilities will be enrolled in any phase of the study. These consent procedures will take place in a private room or office. Written consent and HIPAA forms will be kept in a locked file cabinet within a secure office at each of the 3 sites. Verbal consent will be documented in RedCap & tracking database.

Aim 1: Formative Evaluation/Qualitative Interviews and Design Team Meetings. These interviews and meetings will be done by telephone, with no in-person contact, therefore we will request a waiver of documentation of informed consent as well as waiver of HIPAA. Research staff (RA, PC, or investigator conducting the interviews) will collect verbal informed consent from both the veteran and provider participants for Aim 1. Date of verbal consent obtained will be documented in tracking database or REDCap along with the name of the person who obtained consent.

Aim 2: Intervention. Once the veteran is screened and agrees to enroll, then written informed consent and HIPAA authorization will be obtained at the baseline visit. These visits will be handled by the research assistant at each of the 3 sites. The project coordinator is also trained and able to assist with these visits. All research staff (RAs and PCs) will be up to date on all CITI training and how to obtain and document informed consent.

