Smoking Status		SMOKINGSTATUS_2	0 = Never smoker 1 = Current smoker 2 = Prior smoker
Age		AGE	Continuous
Time since HIV diagnosis	In years	HIVDX_YEARS	Continuous
10-year ASCVD risk score		ASCVDRISK_10YR	Continuous
Lifetime ASCVD risk score		ascvdrisk_lifetime	Continuous

Some of these are specific to clinical trials (based on this [JAMA paper](#)) and some are other are specific to observational studies (based on [STROBE/RECORD](#) guidelines),

Statistical Analysis Plan

Project: A nurse-led intervention to extend the Veteran HIV treatment cascade for cardiovascular disease prevention (V-EXTRA-CVD)

Principal Investigators: [name] PhD

Deliverable (e.g., manuscript, report): Manuscript

ASCVD risk category	<20 (low risk - reference) and >=20 (high risk)	Ascvd_risk_cat	0 = Low risk 1 = High risk
ADI national rank		ADI_NATRANK	Continuous
ADI state rank		ADI_STATERNK	Continuous
Chaos total score		CHAOSTOTAL	Continuous
Loneliness total score		LONELYTOTAL	Continuous
“Out of control” baseline SBP	Baseline SBP \geq 140	SYSTOLICGTE140	0 = No 1 = Yes

Statistical Plan:

Primary Analysis:

The primary outcome will be systolic BP at 12 months and secondary outcome will be non-HDL cholesterol at 12 months, both measured at 4 time-points (0, 4, 8, and 12 months). All BPs used for outcomes will be obtained by a research assistant and cholesterol levels will be measured by lab personnel who are also blinded to treatment group. Because the outcomes are continuous, linear mixed-effects models⁷⁹ (LMM) will be used to examine the differences over time between the study arms. LMM will allow us to implicitly account for the correlation between a patient's repeated measurements over time. The general mean structure of the LMM we will use to examine the hypotheses is:

$$Y_{ij} = \beta_0 + \beta_1 * I(month = 4) + \beta_2 * I(month = 8) + \beta_3 * I(month = 12) + \beta_5 * arm * I(month = 4) + \beta_6 * arm * I(month = 8) + \beta_7 * arm * I(month = 12) + \beta_8 * clinic + \beta_9 * hyperlipidemia$$

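### The plan implies that outcome SBP is read blind to arm, but the role that takes it also randomises participants and educates the control arm only

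*SAP*

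**What the plan says.** **Blinding.** The SAP (Statistical Plan, Primary Analysis) and Protocol 5.6 (Aim 2 analysis) carry the same sentence. Outcome BPs are to be "obtained by a research assistant and cholesterol levels will be measured by lab personnel who are also blinded to treatment group".

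**Randomisation.** Protocol 5.1, Randomization: "The project coordinator and research assistant will be blinded to the randomization schema and will randomize each subject", using a routine built into the tracking software. Protocol 5.2 fixes the time: "Participants will be randomized during the baseline visit". Protocol 5.3 says of the Aim 2 baseline visits: "These visits will be handled by the research assistant at each of the 3 sites". It adds that the project coordinator can assist.

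**Education.** Protocol 5.1 gives control participants usual care with "general prevention education delivered by the research assistant in person at lab collection times (0, 4, 8, and 12 months". For the intervention arm it says: "The in-person visits will be identical to those in the education control group, but without the in-person education material".

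**Outcome BP.** Protocol 5.1 on the 4, 8 and 12 month visits: "Have in-office BP obtained by a trained research assistant using a standardized protocol mentioned above". The visit table in Protocol 5.5 and the Primary Outcomes table in the SAP assign the measurement to the same role.

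**The concern.** SBP at 12 months is the primary endpoint. A reader of the analysis section alone would take both outcomes to be assessed blind. The rest of the protocol describes a measurer whose other duties require knowing the arm.

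What is at stake is how the SBP result may be presented. Assessor blinding is a basic fact about a primary endpoint obtained by study staff, and the SAP names a manuscript as its deliverable. If the sentence is carried over, the manuscript would claim a safeguard that the described procedures do not provide. The SAP itself treats SBP as sensitive to measurement conditions: its missing-data section drops record-based SBP because readings differ between settings. Non-HDL cholesterol is not affected in the same way, because blinding is stated outright for the laboratory.

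**Working it through.** The core of the check is to set the passages side by side. The only arithmetic is a count of contacts and readings.

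**1. What the sentence conveys.** It names two assessors, the research assistant for BP and the laboratory staff for cholesterol. Blinding is stated for the second group only. *Also* needs something to refer back to, and the research assistant is the only other assessor in the sentence. Blinding of the SBP measurer is therefore implied, not stated.

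**2. What the role does.**

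| Task | When | Where stated | Needs or reveals the arm? |
|---|---|---|---|
| Randomises the participant (with the coordinator) | Baseline visit | Protocol 5.1, 5.2, 5.3 | Not blinded to the result by any stated step |
| Educates control participants only | 0, 4, 8, 12 months | Protocol 5.1 | Yes: only controls receive it |
| Takes outcome BP | 4, 8, 12 months | Protocol 5.1, 5.5; SAP Primary Outcomes | Not if blinded, but same role as above |

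**3. What schema blinding covers.** Not knowing the randomisation schema means that the next assignment cannot be foreseen. That is allocation concealment. It says nothing about knowledge of the arm once it is assigned. Whoever educates controls at month 0 must already know who the controls are.

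**4. Contacts before the primary reading.** Education is scheduled at 0, 4, 8 and 12 months. Before the 12-month visit this gives up to 3 contacts (0, 4 and 8) for each control participant and 0 for each intervention participant. A fourth falls at the 12-month visit itself. BP is listed first among the follow-up procedures, but the protocol does not say where education falls relative to it.

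**5. Readings in scope.** With the power section's planning inputs (N = 300; 5%, 10% and 15% missing at 4, 8 and 12 months):

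- 4 months: 300 × 0.95 = 285
- 8 months: 300 × 0.90 = 270
- 12 months: 300 × 0.85 = 255
- Total: 285 + 270 + 255 = 810 expected follow-up SBP values, 255 of them at the primary time point

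These counts show which data the wording covers; they do not measure bias. Some values may come by another route. Protocol 5.2 and 5.5 allow self-measured BP observed over video when staff cannot take it in person. Baseline BP is outside the count, because it may be taken before allocation.

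**6. Search for a separate measurer.** No visible passage assigns a second, arm-blinded person to BP, restricts the measurer's knowledge of arm, or places BP before education as a blinding step.

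**The case against.** **Blinding of the research assistant is never asserted.** This is correct. The plan does not contain two explicit statements in conflict, and *also* may be loose drafting. But if it is loose drafting, the sentence still misleads and needs the same correction.

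**A role is not a person.** This also stands in part. Protocol 5.3 lets the coordinator assist, and its count of three sites does not match the four that enrol. Several passages speak of research assistants in the plural. Those plurals fit a multi-site trial and do not show two people at one site; Protocol 5.2 has clinic providers "refer potentially eligible and interested patients to the site's research assistant", in the singular. The singular is only suggestive, however. The cited BP protocol and the manuals of procedures are not reproduced, so a blinded measurer cannot be excluded.

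**Standardisation may make blinding matter less.** A trained assistant and a standardised protocol reduce the measurer's influence. The visible text does not say whether the device is manual or automated, so how far knowledge of the arm could affect a reading cannot be judged.

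**Stronger readings.** A reader might infer that one individual at each site randomised, educated and measured every participant, or that SBP results are biased towards the intervention. The documents support neither. They describe roles, and they give no size or direction for assessor bias.

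**Conclusion.** The point holds as a mismatch between an implied property of the primary endpoint and the procedures described. Blinded assessment of SBP is unsupported as written; it is not shown to be false. The wording bears on all staff-obtained follow-up SBP values, up to about 810 on the planning assumptions, including about 255 at 12 months. No bias estimate is attached.

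The conclusion rests on two assumptions: that *also* carries its ordinary meaning, and that the documents not reproduced do not provide a separate measurer. If the second fails, one documented statement from the sponsor settles the matter. The point should be fixed because it governs how the primary result may be described. The planned model is unaffected.

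**What to change.** Reconcile the sentence in Protocol 5.6 and the SAP with the duties in Protocol 5.1:

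- Limit the blinding statement to laboratory personnel.
- State who obtained outcome SBP and whether they knew the participant's arm.
- Do not describe SBP as blind-assessed unless the sponsor documents that the readings were taken by existing staff who neither randomised nor educated that participant. Otherwise report SBP assessment as not blinded.
- At any remaining visits, take outcome BP before education is given. This limits influence within the visit but does not restore blinding, because education was given at earlier visits. The documents do not say whether any visits remain.

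The cost is one sentence in two places and one statement in the report, with no new data, staff or analysis. The downsides are a less favourable description of the primary endpoint, unless separate measurers are documented, and a protocol revision. Under the Communication Plan, that revision goes to the central IRB on Form 116.
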